Mobile health (mHealth) interventions can provide on-demand information and support families to improve maternal child health.

mHealth tools, which utilize mobile phones and other wireless technologies to support health, provide an attractive strategy to augment community-based care and connect households to CHV support more efficiently and frequently. More households in low-income countries own a mobile phone than have access to electricity or adequate sanitation.⁸ According to the Communications Authority of Kenya, there are now 46 million phone subscriptions in Kenya, for a national population of 43 million.⁹ **A World Bank report found that Kenyans living at the so-called economic “bottom of the pyramid” reported health information and communication was the service they most wanted to receive through their mobile phones.**¹⁰

Our collaborative team has developed an open-source human-computer hybrid SMS platform, Mobile WACH (Mobile Solutions for Women’s and Children’s Health).¹¹ Mobile WACH sends pre-composed messages to clients at scheduled times. Clients may send messages at any time; a live HCW answers incoming messages, leading to personalized dialogue. The internet-based HCW interface contains a dashboard designed to facilitate HCW management of tasks such as message response, patient tracking, and message translation into English. The system back-end collects SMS metadata such as time stamps and delivery status, as well as data on seminal events such as childbirth. To date, Mobile WACH has been implemented in 7 studies (including 4 randomized controlled trials, RCTs) targeting a range of reproductive, maternal, neonatal and child health outcomes. Scheduled intervention messages were developed for each study based on formative research with the target population,^{12–14} and behavioral theory selected based on the target outcome (Social Cognitive Theory,^{15,16} Theory of Planned Behavior,^{17,18} or Information-Motivation-Behavior Change Theory^{19,20}). All studies also allowed unstructured, personalized dialogue between clients and HCWs. **This suite of studies provides well-developed software and rich data (400,000 SMS) for the proposed project (Table 1).**

[figure not shown]
Table 1. Mobile WACH study summary

Study	Primary outcome	N clients	N SMS			Follow-up period
			Automated system	Personalized nurse	Client	
Mobile WACH XY RCT ¹⁷	Family planning	130	6,852 (144 unique)	3,356	3,577	Preg - 6mo

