Mobile WACH Neo pilot (NEO Pilot) ²⁰	Neonatal health	799	26,021 (62 unique)	13,535	19,952	Preg - 3mo
Mobile WACH X RCT ¹⁶	HIV treatment adherence	276	39,993 (1149 unique)	6,361	10,122	Preg - 2yr
Mobile WACH Neo RCT (NEO RCT)	Neonatal health, Maternal depression	2,500	NA	NA	NA	Preg - 2mo

Automation may enable mHealth interventions to maximize efficiency and adaptability.

Figure. 1. Schematic of just-in-time adaptive intervention design

Adapted from Nahum-Shani et al.²⁷

The public health impact of mHealth interventions in resource-limited settings rests on their ability to achieve the following: (1) reach the people who most need support, (2) deliver efficacious treatment, and (3) reduce the burden on overstretched HCWs. Furthermore, there is increasing recognition that an mHealth intervention may be most efficacious if it is delivered *at the right time and adapts based on the context and response of individual clients*.²¹ This idea is articulated in the paradigm of just-in-time adaptive intervention (JITAI) design.^{22,23} Many mHealth interventions are inherently adaptive – particularly those that include dynamic interaction with a human. The JITAI paradigm

involves formalization of *when* and *how* the intervention should be adapted, by defining decision points, decision rules, and intervention options (Fig. 1). Implementation of this process can only feasibly be accomplished with **automatic, real-time processing of client data** (in the case of SMS interventions, unstructured natural language).^{22,24} **Table 2** summarizes the ways that automation can maximize mHealth intervention impact.

Natural language processing (NLP) enables computational analysis of unstructured language.

Table 2. Applications of automation in mHealth

mHealth function	Application of automation
------------------	---------------------------

REACH people in need	Identify clients when they are in need of support
Deliver EFFECTIVE intervention	Standardize intervention delivery
	Adapt intervention to client status & response
REDUCE BURDEN on HCW	Reduce manual message review & triage
	Prompt, guide or compose HCW messages

[figure not shown]

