 Non-viable neonates	WORKSHEET Neonates

Pregnant women

[WORKSHEET Pregnant Women](#)

a. If you check any of the boxes above, use this space to provide any information that may be relevant for the IRB to consider.

This research proposal is focused specifically on using digital technologies (SMS) to improve neonatal mortality, practice of essential newborn care, care seeking behavior and maternal self-efficacy in Kenya. The research aims are specific to pregnant and postpartum women (including adolescent girls aged 14-17) and their babies. Kenyan regulations consider pregnant women age ≥ 14 emancipated by pregnancy and able to give consent as independent adults.

2.6 Native Americans or non-U.S. indigenous populations. Will Native American or non-U.S. indigenous populations be actively recruited through a tribe, tribe-focused organization, or similar community-based organization?

Indigenous people are defined in international or national legislation as having a set of specific rights based on their historical ties to a particular territory and their cultural or historical distinctiveness from other populations that are often politically dominant.

Examples: a reservation school or health clinic; recruiting during a tribal community gathering

No

Yes

→ If yes, name the tribe, tribal-focused organization, or similar community-based organization. The UW IRB expects that tribal/indigenous approval will be obtained before beginning the research. This may or may not involve approval from a tribal IRB. The study team and any collaborators/investigators are also responsible for identifying any tribal laws that may affect the research.

2.7 Third party subjects. Will the research collect private identifiable information about *other individuals* from the study subjects? Common examples include: collecting medical history information or contact information about family members, friends, co-workers.

"Identifiable" means any direct or indirect identifier that, alone or in combination, would allow you or another member of the research team to readily identify the person. For example, suppose that the research is about immigration history. If subjects are asked questions about their grandparents but are not asked for names or other information that would allow easy identification of the grandparents, then private identifiable information is not being collected about the grandparents and the grandparents are not subjects.

No

Yes

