10 RISK / BENEFIT ASSESSMENT

10.1 Anticipated risks. Describe the reasonably foreseeable risks of harm, discomforts, and hazards to the subjects and others of the research procedures. For each harm, discomfort, or hazard:

- Describe the magnitude, probability, duration, and/or reversibility of the harm, discomfort, or hazard, AND
- Describe how the risks will be reduced or managed. Do not describe data security protections here, these are already described in Question 9.6.
- *Consider possible physical, psychological, social, legal, and economic harms, including possible negative effects on financial standing, employability, insurability, educational advancement or reputation. For example, a breach of confidentiality might have these effects.*
- *Examples of "others": embryo, fetus, or nursing child; family members; a specific group.*
- *Ensure applicable risk information from any Investigator Brochures, Drug Package Inserts, and/or Device Manuals is included in your description.*
- *Do not include the risks of non-research procedures that are already being performed.*
- *If the study design specifies that subjects will be assigned to a specific condition or intervention, then the condition or intervention is a research procedure - even if it is a standard of care.*
- *Examples of mitigation strategies: inclusion/exclusion criteria; applying appropriate data security measures to prevent unauthorized access to individually identifiable data; coding data; taking blood samples to monitor something that indicates drug toxicity.*
- *As with all questions on this application, you may refer to uploaded documents.*

Physical: The study involves no medical interventions therefore we anticipate no risk of physical harm to participants.

Other: SMS: There is a potential risk of disclosure of an individual's person information to others in situations where phones are shared or stolen, which could lead to psychological or physical harm. We will minimize these risks through counseling in the informed consent process and ensuring women understand the type of messaging that will occur. We will remind participants that they may want to erase messages when sensitive or stigmatized topics are discussed.

Access to clinical records: There could be a breach of confidentiality in the process of retrieving participants' medical records. This will be mitigated by training all study staff on data management and storage to ensure confidentiality of sensitive data is maintained.

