10.6 Data and Safety Monitoring. A Data and Safety Monitoring Plan (DSMP) is required for clinical trials (as defined by NIH). If required for this research, or if there is a DSMP for the research regardless of whether it is required, upload the DSMP to **Zipline**. If it is embedded in another document being uploading (for example, a Study Protocol) use the text box below to name the document that has the DSMP. Alternatively, provide a description of the DSMP in the text box below. For guidance on developing a DSMP, see the [ITHS webpage on Data and Safety Monitoring Plans](#).

See attached DSMP.

10.7 Un-blinding. If this is a double-blinded or single-blinded study in which the participant and/or relevant study team members do not know the group to which the participant is assigned: describe the circumstances under which un-blinding would be necessary, and to whom the un-blinded information would be provided.

NA

10.8 Withdrawal of participants. If applicable, describe the anticipated circumstances under which participants will be withdrawn from the research without their consent. Also, describe any procedures for orderly withdrawal of a participant, regardless of the reason, including whether it will involve partial withdrawal from procedures and any intervention but continued data collection or long-term follow-up.

NA

10.9 Anticipated direct benefits to participants. If there are any direct research-related benefits that some or all individual participants are likely to experience from taking part in the research, describe them below:

Do not include benefits to society or others, and do not include subject payment (if any). Examples: medical benefits such as laboratory tests (if subjects receive the results); psychological resources made available to participants; training or education that is provided.

Women may benefit directly from the education that will be provided as part of the study. The intervention could potentially enhance women’s engagement with the health care system and optimize their follow-up and retention in care. Women will receive additional counseling, information and support. This has potential to improve both women’s and infants’ clinical outcomes.

10.10 Return of individual research results.

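### Does Section 10.1 need a change to the plan because it expects no physical harm and does not name errors of the urgency model?

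*Protocol*

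**What the plan says.** Section 10.1 asks for each foreseeable risk of the research procedures and instructs the applicant: "Describe how the risks will be reduced or managed". The answer under its physical heading is "The study involves no medical interventions therefore we anticipate no risk of physical harm to participants". The following paragraph, on shared or stolen phones, describes disclosure of personal information "which could lead to psychological or physical harm". It gives two mitigations: counselling at consent and a reminder that messages can be erased. The other listed risks are access to clinical records, loss of confidentiality in interviews and focus groups, and distress from sensitive topics. An error of the urgency model is not listed.

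Elsewhere, Section 2.5a states the purpose: "This research proposal is focused specifically on using digital technologies (SMS) to improve neonatal mortality". Section 10.9 says of the counselling and support: "This has potential to improve both women’s and infants’ clinical outcomes".

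On workflow, Section 1.8a describes the existing platform, where "a live HCW answers incoming messages, leading to personalized dialogue", and adds that "The system back-end collects SMS metadata such as time stamps and delivery status". Table 2 there, on uses of automation in mHealth, includes "Reduce manual message review & triage". Section 1.8b sets out two candidate uses of a model: a triage use, in which fewer messages are reviewed, and a prioritising use, in which the unflagged messages are read afterwards. Section 1.5 has nurses test three models in Aim 1 and design the display in Aim 2. In Aim 3 messages are classified automatically, and response times to urgent and non-urgent messages are compared with the NEO trial. Section 10.6 refers to an attached data and safety monitoring plan, which is not shown.

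**The concern.** A reader of 10.1 meets a flat denial of physical risk and, a few lines later, a physical risk. The reason offered for the denial, that nothing medical is done, also sits awkwardly beside an application that hopes to affect neonatal mortality. If a prompt reply can help, a late one can forgo that help.

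The omission looks more serious than the wording. All four listed risks could have been written for the conventional system. What is new in AI-NEO is a classifier acting on live messages, and its obvious failure is an urgent message left unflagged and answered later than it would otherwise have been. If 10.1 neither names this nor says how it is handled, the ethics board may weigh hoped-for benefit against an understated risk. The pilot might also end without a count of urgent messages the model missed, or of how long they waited, although a decision to scale up would want both.

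**Working it through.** **Wording.** The physical sentence and the SMS paragraph cannot both be read literally. They stand in the same answer, however, and the second gives the risk and its mitigation. The board therefore does not read a statement of zero physical risk. The evident sense of the first sentence is that no treatment or procedure is given that could injure directly.

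**Benefit statements.** Section 2.5a states an aim and Section 10.9 a potential. Neither contradicts an expectation of no physical harm. Section 5.1 keeps all clinical care in the existing maternal and child health services, so a slower reply reduces an added support and does not replace care.

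**Is model error uncontrolled?** Aim 1 selects among three models by sensitivity and specificity against nurses, although no minimum is set. Section 5.1 gives three examples of display: a different colour, sorting to the top, or a different part of the screen. None removes a message. Aim 3 measures response time for non-urgent messages too, which implies that they are answered. The foreseeable failure is delay, not silence.

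**Are the workflow passages in conflict?** The description in 1.8a is of the present platform, Table 2 is a general list, and 1.8b names candidate uses. None is a rule for the pilot. The choice is left to Aims 1 and 2, which is the staged design.

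**How many misses?** The documents give message volumes only (Table 1, NEO pilot). The share urgent and the sensitivity below are assumptions.

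- Client messages per woman: 19,952 / 799 = 24.97. For 80 women: 80 × 24.97 ≈ 2,000.
- Scaling with automated messages instead: 19,952 / 26,021 = 0.767 client messages per automated one. The Section 5.1 schedule, with delivery at the due date, gives at most 10 + 14 + 14 + 14 = 52 automated messages, so 80 × 52 × 0.767 ≈ 3,190. This needs every woman enrolled at 28 weeks.
- The 2,000 is not a lower bound. The NEO pilot followed women to 3 months, whereas SMS here stop at 6 weeks postpartum.
- With 5% urgent, 2,000 × 0.05 = 100 urgent messages. If misses are independent, P(at least one) = 1 − 0.99^100 = 0.63 at sensitivity 0.99, and 1 − 0.95^100 = 0.994 at 0.95.
- With half as many, 50 urgent messages: 1 − 0.99^50 = 0.39, and 1 − 0.95^50 = 0.92.

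Some miss is therefore foreseeable, as with any imperfect classifier. No actual count follows, and nothing in the documents gives the length of a delay.

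**Would a correction button help?** One suggestion is a one-tap correction of the flag when the nurse opens a message. At an assumed 2 to 3 seconds each, this costs 2,000 × 2 s = 1.1 hours to 3,200 × 3 s = 2.7 hours in all. It is cheap, but it acts after the message has been opened, when any delay is already past. Nurses who see the flag may tend to agree with it, and unopened messages would not be counted, so the result would be a probable lower bound and not an estimate of sensitivity. It would also add a step to the AI-NEO workflow alone, while that workflow is being timed against NEO.

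**The case for a change.** The strongest case for a change needs no arithmetic. Two adjacent statements disagree, the form asks for every foreseeable risk with its management, and the one risk peculiar to this intervention is absent. The only model reported near a target region is near the triage one, where fewer messages are reviewed, and Aim 1 sets no minimum sensitivity. Section 10.1 allows reference to uploaded documents but makes none on this point. Correcting it would take a few sentences.

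The mismatch and the omission stand, and an editor revising the form for other reasons could tidy both. What does not stand is the step from there to a defect in the trial. New sentences in 10.1 would record a risk; they would not change who is enrolled, what is measured, or what can be concluded. Whether the pilot yields a count of missed urgent messages depends on how messages are labelled for the response-time comparison. NEO runs without the model, so its messages must be labelled in some other way. If AI-NEO messages are labelled in the same way, the count follows from stored data. That detail commonly belongs in an analysis plan, and none is shown here.

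**Conclusion.** No change to the plan is called for. The clash between the physical sentence and the SMS paragraph is a clerical slip, since the risk is disclosed and mitigated in the same answer. Leaving model error out of 10.1 is a gap in disclosure, partly covered by validation in Aim 1 and by the kinds of display proposed for Aim 2. The statements of aim and potential benefit contradict nothing. The button is an optional measurement feature that the Aim 2 nurses may consider; it serves neither of the pilot's stated ends, acceptability and response time, and does not shorten a delay.

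The size of the matter cannot be fixed. At least one missed urgent message has probability 0.39 to 0.994 over the cases worked above, all of which rest on assumed prevalence and sensitivity and on independent misses. The judgement assumes that unflagged messages remain visible to nurses, as in every display example given. If Aims 1 and 2 led to a display that took unflagged messages out of view, the question would deserve a fresh look. The unseen monitoring plan and Aim 3 consent form may already address it.

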11 ECONOMIC BURDEN TO PARTICIPANTS

11.1 Financial responsibility for research-related injuries. Answer this question only if the lead researcher is not a UW student, staff member, or faculty member whose primary paid appointment is at the UW.

For each institution involved in conducting the research: Describe who will be financially responsible for research-related injuries experienced by subjects, and any limitations. Describe the process (if any) by which participants may obtain treatment/compensation.

NA

11.2 Costs to subjects. Describe any research-related costs for which subjects and/or their health insurance may be responsible (examples might include: CT scan required for research eligibility screening; co-pays; surgical costs when a subject is randomized to a specific procedure; cost of a device; travel and parking expenses that will not be reimbursed).

No costs

12 RESOURCES

12.1 Faculty Advisor. (For researchers who are students, residents, fellows, or post-docs.) Provide the following information about the faculty advisor.

- Advisor's name
- Your relationship with your advisor (for example: graduate advisor; course instructor)
- Your plans for communication/consultation with your advisor about progress, problems, and changes.

NA

12.2 UW Principal Investigator Qualifications. Upload a current or recent Curriculum Vitae (CV), Biosketch (as provided to federal funding agencies), or similar document to the Local Site Documents page in Zipline. The purpose of this is to address the PI's qualifications to conduct the proposed research (education, experience, training, certifications, etc.).

For help with creating a CV, see http://adai.uw.edu/grants/nsf_biosketch_template.pdf and <https://education.uwmedicine.org/student-affairs/career-advising/year-4/residency-applications/curriculum-vitae/>

The CV will be uploaded.

12.3 UW Study team qualifications. Describe the qualifications and/or training for each UW study team member to fulfill their role on the study and perform study procedures. (You may be asked about non-UW study team members during the review; they should not be described here.) You may list these individuals by name, however if you list an individual by name, you will need to modify this application if that individual is replaced. Alternatively, you can describe study roles and the qualifications and training the PI or study leadership will require for any individual who might fill that role. The IRB will use this information to assess whether risks to subjects are minimized because study activities are being conducted by properly qualified and trained individuals.

Describe: The role (or name of person), the study activities they will perform, and the qualifications or training that are relevant to performing those study activities.

Examples:

Research Study Coordinator: Obtain consent, administer surveys, blood draw. Will have previous experience coordinating clinical research and be a certified phlebotomist in WA.

Undergraduate Research Assistant: Obtain consent, perform all study procedures. Will have had coursework in research methods, complete an orientation to human subjects protections given by the department, and will receive training from the PI or the graduate student project lead on obtaining consent and debriefing subjects.

Acupuncturist: Perform acupuncture procedures and administer surveys. Must be licensed with WA State DoH and complete training in administering research surveys given by the project director, an experienced survey researcher.

Co-Investigator: Supervise MRI and CT scan procedures and data interpretation, obtain consent. MD, specialty in interventional radiology and body imaging. 5-years clinical research experience.

Mentors: Provide technical assistance and guidance to the principal investigator in developing and executing the study. This project is an NIH mentored career development award. Mentors have expertise in clinical trial conduct, digital health, and computer science.

Site PI: Provide leadership and close guidance in study implementation. Medical doctor with 20 years' experience in clinical medicine, and women's health research in Kenya.

Obstetrics and Gynecology Collaborator: Provide technical assistance on pilot intervention development. Medical doctor with 15 years' experience in clinical medicine, women's health research in Kenya and mHealth interventions.

Computer Science Collaborators: Provide technical and analytical expertise, including developing natural language processing models, supporting human-centered design activities, and developing SMS system software. Masters or PhD degree training and 5-10 years' expertise in human-centered design, computer science, and software development.

12.4 Study team training and communication. Describe how it will be ensured that each study team member is adequately trained and informed about the research procedures and requirements (including any changes) as well as their research-related duties and functions.

There is no study team.

The study team will participate in an initial training at study launch to ensure all team members understand study procedures. The team will also have weekly calls and use e-mail communication to share any protocol updates.

13 OTHER APPROVALS, PERMISSIONS, and REGULATORY ISSUES

13.1 Approvals and permissions. Identify any other approvals or permissions that will be obtained. For example: from a school, external site/organization, funding agency, employee union, UW Medicine clinical unit.

Do not attach the approvals and permissions unless requested by the IRB.

Kenyatta National Hospital Ethics and Research Committee

13.2 Financial Conflict of Interest. Does any UW member of the team have ownership or other Significant Financial Interest (SFI) with this research as defined by [UW policy GIM 10](#)?

No

Yes → If yes, has the Office of Research made a determination regarding this SFI as it pertains to the proposed research?

No → If no, contact the Office of Research [contact], [contact]) for guidance on how to obtain the determination

Yes → If yes, upload the Conflict Management Plan for every UW team member who has a FCOI with respect to the research, to **Zipline**. If it is not yet available, use the text box to describe whether the Significant Financial Interest has been disclosed already to the UW Office of Research and include the FIDS Disclosure ID if available.
